4.2.2 Exclusion Criteria

1. Subjects with moderately or severely deteriorated lung function in the 4 weeks before the Week 1 (baseline) visit
2. Subjects whose percentage of forced expired volume in 1 second (%FEV₁) after inhalation of a bronchodilator is <30% during the screening period
3. Subjects who have undergone lung transplantation or liver transplantation
4. Subjects who have undergone any lung surgery (excluding lung biopsy) in the past 2 years
5. Subjects with increased liver enzymes (AST, ALT, and ALP) ≥ 2.5 times the upper limit of normal
6. Subjects with severe complications including but not limited to congestive heart failure and liver cirrhosis
7. Subjects who have developed any malignant tumor (including malignant melanoma; however, other forms of skin cancer are excluded) in the past 5 years
8. Pregnant women, breastfeeding women, or women of childbearing potential who do not intend to use effective contraceptive methods (use of oral, injection, or implant hormonal contraceptives; placement of an intrauterine device (IUD) or intrauterine contraceptive system; concomitant use of spermicidal foam, gel, film, cream, suppository and condoms or cervical caps; male sterilization; or abstinence) throughout the trial period or male subjects who have a partner who is of childbearing potential and is unwilling to use effective contraceptive methods throughout the trial period.
9. Subjects with a past history of HAV, HBV, HCV, or HIV infection, or subjects currently presenting with clinical signs or symptoms suggestive of such infection
10. Subjects with a smoking history in the past 6 months, or subjects tested positive for urinary cotinine levels at the screening visit
11. Subjects participating in another clinical trial within 4 weeks before the Week 1 (baseline) visit
12. Subjects with a history of anaphylactic or severe systemic reactions to any plasma derived alpha₁-PI product or other blood products
13. Subjects who have continuously received any systemic steroid therapy at a prednisone-equivalent dose >5 mg/day within 4 weeks before the Week 1 (baseline) visit (Note: inhaled steroids are not regarded as systemic steroids)
14. Subjects who have used any systemic or aerosolized antibiotic drug for the treatment of COPD exacerbation within 4 weeks before the Week 1 (baseline) visit

15. Subjects with a previous or current diagnosis of selective, severe IgA deficiency
16. Subjects who are mentally challenged and cannot independently give consent
17. Subjects who have difficulty in adhering to the protocol or its procedures in the opinion of the investigator
18. Subjects who have medical conditions that may confound the results of this clinical trial or may endanger other subjects during the participation in this clinical trial in the opinion of the investigator

<Rationale for establishing the exclusion criteria>

1. This criterion has been established to exclude subjects with this medical condition because the condition will affect pulmonary function tests (PFTs) and clinical laboratory tests, thereby precluding appropriate safety evaluation.
2. This criterion has been established to determine the range of percentage of forced expired volume in 1 second (%FEV₁) to be excluded.
3. Same as 1 above.
4. Same as 1 above.
5. This criterion has been established to exclude subjects with any underlying disease that may affect clinical laboratory values and safety evaluation.
6. Same as 5 above.
7. Same as 5 above.
8. This criterion has been established because animal reproduction studies have not been conducted with Alpha₁-PI, the safety of Alpha₁-PI in pregnant women and their fetuses as well as its effects on fertility have not been established yet, and no results on the excretion of Alpha₁-PI into breast milk are available.
9. Same as 1 above.
10. This criterion has been established to exclude smokers who may be at risk for further deterioration of lung function and lung damage.
11. This criterion has been established to exclude any effect on the evaluation of adverse events and safety of this investigational drug.
12. Same as 11 above.
13. This criterion has been established to reduce clinical changes associated with the use of concomitant drugs and exclude factors that may affect symptomatic improvement.
14. Same as 1 above.
15. Same as 11 above.
16. This criterion has been established to exclude subjects in whom it is difficult to confirm whether they intend to consent or not.
17. This criterion has been established to exclude subjects who cannot adhere to the protocol.
18. Same as 11 above.

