		
 6. Subjects with severe complications, including but not limited to, congestive heart failure and liver cirrhosis 7. Subjects who have developed any malignant tumor (including malignant melanoma; however, other forms of skin cancer are excluded) in the past 5 years 8. Pregnant women, breastfeeding women, or women of childbearing potential who do not intend to use effective contraceptive methods throughout the trial period or male subjects who have a partner who is of childbearing potential and is unwilling to use effective contraceptive methods throughout the trial period. 9. Subjects with a past history of HAV, HBV, HCV, or HIV infection, or subjects currently presenting with clinical signs or symptoms suggestive of such infection 10. Subjects with a smoking history in the past 6 months, or subjects tested positive for urinary cotinine levels at the screening visit 11. Subjects participating in another clinical trial within 4 weeks before the Week 1 (baseline) visit 12. Subjects with a history of anaphylactic or severe systemic reactions to any plasma derived alpha₁-PI product or other blood products 13. Subjects who have continuously received any systemic steroid therapy at a prednisone-equivalent dose >5 mg/day within 4 weeks before the Week 1 (baseline) visit (Note: inhaled steroids are not regarded as systemic steroids) 14. Subjects who have used any systemic or aerosolized antibiotic drug for the treatment of COPD exacerbation within 4 weeks before the Week 1 (baseline) visit 15. Subjects with a previous or current diagnosis of selective, severe IgA deficiency 16. Subjects who are mentally challenged and cannot independently give consent 17. Subjects who have difficulty in adhering to the protocol or its procedures in the opinion of the investigator 18. Subjects who have medical conditions that may confound the results of this clinical trial or may endanger these subjects during their participation in this clinical trial in the opinion of the investigator
	Investigational Drug	Alpha-1 MP: Sterile, lyophilized preparation (each vial contains approximately 1000 mg of functionally active alpha ₁ -PI)

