4.2. Selection of Subject Population

Eligible subjects must provide written consent to participate in this clinical trial of their own free will after being fully informed of the contents of the trial based on the written information and informed consent form.

After obtaining written informed consent from each subject, the investigator or subinvestigator will screen the subject within 21 days before the first investigational drug infusion. The investigator will assess subject eligibility based on the inclusion criteria and the exclusion criteria below.

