4.7.2.2 Treatment period

During the 8-week treatment period, subjects will receive a total of 8 weekly intravenous infusions of 60 mg/kg of Alpha-1 MP. Weekly infusions of Alpha-1 MP will be given at the scheduled Week 1 (baseline), 2, 3, 4, 5, 6, 7, and 8 visits at each study center. Visit dates after the Week 1 (baseline) visit will be arranged at 1-week intervals as specified in the protocol according to the actual date of the Week 1 (baseline) visit (± 1 day).

Subjects meeting all of the inclusion criteria and not meeting any of the exclusion criteria will make the Week 1 (baseline) visit within 21 days after the screening visit. Subjects considered eligible will receive the initial intravenous infusion (intravenous drip) of Alpha-1 MP at the Week 1 (baseline) visit.

The 1-week PK evaluation period will start at the Week 8 visit and end at the Week 9 visit. At the Week 8 visit, subjects will undergo blood sampling for PK evaluation immediately before the intravenous infusion of Alpha-1 MP; immediately after the intravenous infusion; and at 15 minutes, 2, 4, and 8 hours after completion of the intravenous infusion. Subjects will visit the study center 1 day (PK1), 2 days (PK2), and 5 days (PK5) after the Week 8 visit to provide PK evaluation blood samples at 24 ± 4 hours (1 day), 48 ± 4 hours (2 days), and 120 hours ± 1 day (5 days), respectively, after the intravenous infusion of Alpha-1 MP at the Week 8 visit. The date of Week 9 visit will be scheduled in the week specified in the protocol according to the actual date of the Week 1 (baseline) visit (± 1 day).

Visit	Trial Procedures and Evaluations

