5.1 Warnings/Precautions

Alpha-1 MP is human alpha₁-PI produced by a modification of the Prolastin process and is approved as Prolastin-C for 60 mg/kg weekly IV administration in the US, Canada, Columbia, Argentina, and Turkey. For complete Alpha-1 MP safety information, refer to the current Alpha-1 MP IB.

Immunoglobulin E-mediated anaphylactic reactions to plasma-derived, alpha₁-PI preparations may occur in recipients (27) with or without documented prior histories of severe allergic reactions to blood products. Very rarely, an anaphylactoid reaction may occur in subjects with no prior history of severe allergic reactions to plasma-derived alpha₁-PI administration (28).

Individuals with selective IgA deficiency should not receive alpha₁-PI since these subjects may experience severe reactions, including anaphylaxis, to IgA which may be present in the preparation.

It is not known whether alpha₁-PI is excreted in human breast milk, can cause fetal harm when administered to pregnant women, or can affect reproductive capacity. Subjects who are pregnant must not enter the study, and subjects who become pregnant during the study must be withdrawn.

Overdose with plasma-derived alpha₁-PI has not been reported. In an overdose situation, supportive care should be given and the subject managed accordingly.

The manufacturing process for all Grifols plasma-derived products begins with the screening of plasma donors and the testing of individual plasma donations and plasma manufacturing pools for specific markers of viral infection. To provide additional assurance of the pathogen safety margin of the final product, in vitro laboratory spiking studies were performed to validate the capacity of key steps of the Alpha-1 MP manufacturing process to inactivate and/or remove pathogenic agents.

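### Exclusion 15 bars only severe selective IgA deficiency, but Section 5.1 warns against treating any selective IgA deficiency; exclusion 18 also differs between the synopsis and Section 4.2.2

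*Protocol*

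**What the plan says.** Exclusion 15 reads the same in the protocol synopsis and in Section 4.2.2: "Subjects with a previous or current diagnosis of selective, severe IgA deficiency". The rationale list in Section 4.2.2 gives it no reason of its own. It points back to the rationale for exclusion 11, which is to avoid effects on the evaluation of adverse events and safety.

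Section 5.1 states the product warning more broadly. "Individuals with selective IgA deficiency should not receive" alpha1-PI, it says, "since these subjects may experience severe reactions, including anaphylaxis, to IgA which may be present in the preparation".

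Two passages make the criteria list the operative gate. Section 4.2: "The investigator will assess subject eligibility based on the inclusion criteria and the exclusion criteria below". Section 4.7.2.2: "Subjects meeting all of the inclusion criteria and not meeting any of the exclusion criteria will make the Week 1 (baseline) visit", where the first infusion is given.

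Exclusion 18 has two versions. The synopsis covers medical conditions that "may endanger these subjects during their participation in this clinical trial in the opinion of the investigator". Section 4.2.2 covers conditions that "may endanger other subjects during the participation in this clinical trial in the opinion of the investigator".

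**The concern.** Section 5.1 and exclusion 15 both address selective IgA deficiency, but they draw the line in different places. In Section 5.1 the adjective *severe* describes the reaction that may follow; in exclusion 15 it describes the deficiency. A site that works from the list would find a patient with a known, non-severe selective deficiency eligible, although the protocol's own warning says such a patient should not be treated.

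Safety is the primary objective (Section 3.1), and anaphylaxis is the harm that Section 5.1 names. The list that decides who is infused should be no looser than the warning about who should not be.

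The general clause in exclusion 18 is the natural backstop for such a patient, because the danger is to that patient alone. Read literally, the Section 4.2.2 version omits the candidate's own risk.

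**Working it through.** No arithmetic applies. The check sets the texts side by side and follows one hypothetical candidate through them.

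**The two IgA rules**

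| Place | Who is barred | Severity limit |
|---|---|---|
| Synopsis, exclusion 15 | Diagnosed selective IgA deficiency | Severe only |
| Section 4.2.2, exclusion 15 | Diagnosed selective IgA deficiency | Severe only |
| Section 5.1 | Selective IgA deficiency | None |

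The protocol does not say what makes the deficiency severe. Table 4-2 lists no IgA measurement, so a site has neither a threshold nor a protocol test with which to apply one.

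**A candidate with a diagnosed, non-severe selective IgA deficiency and no earlier reaction to a blood product**

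1. Exclusion 15: not met, because the deficiency is not severe.
2. Exclusion 12: not met. It needs a history of an anaphylactic or severe systemic reaction to a plasma-derived alpha1-PI product or another blood product. Section 5.1 itself warns that anaphylactic reactions can occur without a documented history of severe allergic reactions to blood products.
3. Exclusion 6: not clearly met. It concerns severe complications, and applying it to a non-severe deficiency is a matter of judgement.
4. Exclusion 18, endangerment limb: met in the synopsis version if the investigator so judges. Not met in the Section 4.2.2 version read literally, since the patient's deficiency endangers nobody else.
5. Exclusion 18, confounding limb: available in both versions, but discretionary.
6. Week 1 re-evaluation (Section 4.7.2.2): applies the same inclusion and exclusion criteria, so it does not close the gap.
7. Section 6.1, criterion (2): allows withdrawal on the investigator's judgement, but it governs discontinuation rather than entry.
8. Section 5.1: says the patient should not be treated.

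Only step 8 covers this patient by name. Steps 3, 4, 5 and 7 depend on judgement, and none of those clauses mentions IgA deficiency.

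**Exposure if admitted.** Sections 4.3.3.1 and 4.4.3 schedule 8 weekly infusions of 60 mg/kg, or 8 × 60 = 480 mg/kg in total. Section 4.1.1 then offers at least another year of treatment in the extension trial.

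**How the protocol handles a comparable warning.** Section 5.1 also says that pregnant subjects must not enter. Exclusion 8 carries that over in full, whereas exclusion 15 narrows the IgA warning.

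**Exclusion 18.** The two versions otherwise express the same clause. Its rationale, shared with exclusion 11, concerns the evaluation of adverse events and safety. A condition in one participant that endangers the others is an unlikely target in an infusion study. Treating the Section 4.2.2 wording as an editing or translation slip is an inference, but the synopsis supports it.

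**The case against.** The strongest reply is that the protocol already bars this patient. Section 5.1 is protocol text, Section 10.1 commits the investigator to the protocol, and Section 4.3.5 requires the drug to be used as the protocol directs. A careful investigator who reads the whole document would probably not dose the patient. On this view the defect is a drafting mismatch.

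There are supporting points. Exclusion 12 removes anyone with a prior serious reaction. The confounding limb of exclusion 18 is intact in both places and could fairly be used. Infusions are given on site under supervision, with at least 30 minutes of observation afterwards. The investigator's brochure, to which Section 5.1 refers, may define or limit the IgA warning, and the protocol is labelled as corresponding to Ver1.5J; neither document is available here. No document shows that non-severe selective IgA deficiency is a recognised group among these patients. The absence of an IgA test adds little, because exclusion 15 works on an existing diagnosis and undiagnosed patients are unaffected either way.

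Most of this stands as a limit on the practical effect. It does not reconcile the two rules. Sections 4.2 and 4.7.2.2 base eligibility on the list, exclusion 12 misses patients with no earlier reaction, and the remaining clauses rest on judgement. If the severity limit was deliberate, Section 5.1 is too broad and the sections still need to be brought into line. The exclusion 18 point is editorial and secondary.

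**Conclusion.** The concern holds. Exclusion 15 is narrower than the warning in Section 5.1, and the protocol gives no definition of *severe* and no reason for the narrowing. The list, read alone, lets through a patient whom the warning says should not be treated.

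The size cannot be put as a rate, because the documents give no frequency for non-severe selective IgA deficiency. The case is likely rare: Section 1.1 reports 16 documented patients in a 2000 survey, and Section 8.2 sets a minimum of 3 subjects. The consequence for an affected patient could be serious. The issue is eligibility and subject safety; no endpoint, estimate or analysis changes.

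This rests on the English text as supplied, and on reading *severe* in exclusion 15 as a real restriction on the deficiency. The sponsor should make the change. Exclusion 15 carries the weight, and exclusion 18 is a wording correction alongside it.

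**What to change.** - **Exclusion 15:** delete *severe* in Section 4.2.2 and in the synopsis, so that both cover selective IgA deficiency without a severity limit, as Section 5.1 does. If the sponsor's medical lead can justify a threshold, define it and use it in all three places.
- **Exclusion 18, Section 4.2.2:** adopt the synopsis wording, so that the clause covers conditions that "may endanger these subjects during their participation in this clinical trial in the opinion of the investigator".
- **Japanese text:** check both points in Ver1.5J and correct them there if they recur.

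The cost is a wording amendment to two criteria, with no new test, visit or analysis. At most it excludes a rare extra candidate from a very small pool, and Section 5.1 already says that candidate should not receive the drug.

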4.3. Investigational Drug

4.3.1 Investigational Drug

4.3.1.1 Investigational drug code

Alpha-1 MP

4.3.1.2 Investigational drug name

Alpha-1 MP

4.3.1.3 Content and dosage form

Alpha-1 MP is a stable, sterile, lyophilized preparation of human alpha₁-PI, also known as α₁-antitrypsin. Alpha-1 MP is supplied as a white to beige, lyophilized powder contained in a glass vial. Each vial of Alpha-1 MP contains the labeled amount of functionally active alpha₁-PI in milligrams per vial (each vial contains approximately 1,000 mg of functionally active alpha₁-PI). Alpha-1 MP contains no preservatives. Alpha-1 MP is reconstituted using a dissolving solution (20 mL of water for injection) as instructed in the Pharmacy Manual. Alpha-1 MP must be administered by an intravenous route.

Further information on the investigational drug is provided in the investigator's brochure.

4.3.1.4 Composition of the Preparation

The composition of the preparation per vial is shown in Table 4-1.

Table 4-1 Composition of Alpha-1 MP Preparation

Component	Content (per vial)	Quality standards
Alpha ₁ -Proteinase Inhibitor (Human)	Nominal 1,000 mg	WHO Standard
NaH ₂ PO ₄	0.4 mmol	United States Pharmacopeia
NaCl	2.0 mmol	United States Pharmacopeia

4.3.2 Investigational Drug Labeling

4.3.2.1 Packaging

An individual package contains 10 labeled, transparent vials.

4.3.2.2 Labeling

The labels for the investigational drug on an individual package and a vial include the following information: the statements "For Investigational Use", investigational drug name, protocol No.,

instructions for use, expiration date, serial number, storage conditions, quantity, and sponsor's name and address. Sample labels on an individual package and a vial are shown below.

GRIFOLS Protocol: GTI1401
 
Alpha1-Proteinase Inhibitor (Human), Modified Process (Alpha-1 MP)
 
Contents:
 
· 10 Alpha-1 MP Vials· 12 Filter Needles· 12 Transfer Needles 
SHIP AND STORE AT TEMPERATURES NOT TO EXCEED 25°C. DO NOT FREEZE.
 
Reconstitute with 20 mL Sterile Water for Injection for a vial. For intravenous administration only.
 
Dosage per Protocol. For Clinical Trial Use Only.
 
Site No.: _____ Investigator's Name: _____
 
LOT EXP. mg α1-PI / vial
 
Grifols Japan K.K. [name]

Figure 4-2 Sample Labeling for the Investigational Drug

Protocol: GTI1401
 
Alpha 1-Proteinase Inhibitor (Human), Modified Process (Alpha-1 MP)
 
Store at temperatures not to exceed 25°C. Do not freeze. Reconstitute with 20 mL Sterile Water for Injection For intravenous administration only. Dosage per Protocol. For Clinical Trial Use Only.
 
Site No.: _____ Investigator's Name: _____ Patient ID: _____
 
LOT EXP. mg α1-PI / vial
 
Grifols Japan K.K. [name]

--

Figure 4-3 Sample Labeling for the Investigational Drug

4.3.3 Dose and Dosage Regimen

4.3.3.1 Dose and dosage regimen

Subjects will receive a total of 8 IV infusions of 60 mg/kg Alpha-1 MP administered weekly. The prescribed infusion rate for Alpha-1 MP is not to exceed 0.08 mL/kg/min as determined by the response and comfort of the subject. The recommended dose for this trial takes approximately 15 minutes per IV bag to infuse (based on ~70 kg subject).

4.3.3.2 Rationale for the dose

The recommended dose of Alpha-1 MP (commercially available as Prolastin-C) is 60 mg/kg body weight administered once weekly. Alpha-1 MP is currently approved for 60 mg/kg weekly IV administration in the US, Canada, Columbia, Argentina, and Turkey. As such, Alpha-1MP at a dose of 60 mg/kg body weight will be used in this study.

4.3.3.3 Rationale for the dosage regimen

Given that Alpha-1 MP has a serum half-life of approximately one week in Caucasians (see Section 1.3), weekly infusion is the preferable treatment regimen. Furthermore, the recommended dose of Alpha-1 MP is 60 mg/kg body weight administered once weekly. In

this study, subjects will receive IV-administered Alpha-1 MP once weekly for 8 weeks for a total of 8 infusions.

4.3.4 Storage of the Investigational Drug

Alpha-1 MP should be stored at a temperature not to exceed 25°C. Do not freeze. Alpha-1 MP must be stored in a secure area accessible only to designated study site personnel until dispensed for the study subject.

Alpha-1 MP should be kept at room temperature after reconstitution and should be administered within 3 hours after reconstitution.

Additional details are provided in the Pharmacy Manual.

4.3.5 Accountability of the Investigational Drug

Alpha-1 MP is to be used only for the study in accordance with the directions given in this protocol. The Primary Pharmacist responsible for management of the Investigational Product at the site, is responsible for the distribution of Alpha-1 MP in accordance with directions given in the protocol and Pharmacy Manual.

The Primary Pharmacist is responsible for maintaining accurate records of Alpha-1 MP for his/her site. Alpha-1 MP inventory/dispensing documentation verifying the receipt, dispensing, destruction, or return must be maintained and kept current by the Investigator, or designee. The inventory must be made available for inspection by the study monitor. Alpha-1 MP supplies must be accounted for by the study monitor and inventory/dispensing logs must be verified by the monitor prior to Alpha-1 MP return or destruction. Written documentation of all used and unused inventory is required. At the end of the study, a copy of the inventory/dispensing log(s) will be retrieved by the monitor and returned to Grifols Japan K.K.

